7.1. Demographic, Baseline and Medical History

Baseline characteristics of the primary analysis population will be presented. These characteristics include demographics such as age, sex, race, and ethnicity as well as medical history and co-morbidities including COVID status.

Descriptive statistics for continuous variables will include the mean, standard deviation, N, median, and range in the form of a minimum and maximum. Categorical data will be summarized using percentages and the count (numerator) and N (denominator) used to calculate the percentage.

7.2. Subject Accountability

Subject accountability will be presented in tabular form. This table will summarize how many subjects were screened and enrolled into this trial. This table will also summarize the number of subjects withdrawing from the study and the reason for withdrawal.

Screen failures are defined as subjects who consent to participate in the clinical trial, but who do not subsequently wear a Jewel (Jewel does not enter Monitor Mode). These subjects will not be included in any study analyses. A minimal set of screen failure information will be captured, including demographics, screen failure details, and eligibility criteria.

8. Sample Size Estimation

A Scientific Literature Review was performed to determine a clinically meaningful rate for inappropriate shocks and safety events. This is documented in the Report of Prior Investigations.

The estimated power for the primary effectiveness endpoint analysis is based off Monte-Carlo simulations. In order to assess power, 10,000 studies were simulated using various study sizes. For each subject within a study, a random wear time was assigned using a normal distribution with an average of 2.5-months and a standard deviation of 0.5 month. Each subject was also assigned a time to inappropriate shock using an exponential distribution. If the time to inappropriate shock is greater than the wear time, then that subject did not experience an event during the course of the trial. If the time to inappropriate shock is less than the wear time, then that subject is considered to have had an event. For subjects experiencing an event, wear time beyond the time to inappropriate shock is in not counted in the simulations. Since inappropriate shock is a rare event, some of the simulated studies had no subjects that experienced an inappropriate shock. When this happened, the study with zero total events was given a total of 0.5 events in order to allow for convergence of the models. Each study was then used to fit a Poisson regression model from which an estimated rate of inappropriate shock along with a one-sided 98% upper bound on that rate was generated. If

that upper bound was below the performance goal, then that study is considered successful, otherwise it is considered to have failed. Adding up the number of successful trials gives an estimate of power for a given sample size.

For the purposes of sample size calculation, the expected inappropriate shock rate was set to 0.37 shocks per 100 subject-months. This is the inappropriate shock rate observed in the NEJM published LifeVest "VEST" RCT² and it is assumed that the Jewel P-WCD will have a similar or better inappropriate shock rate. Assuming an expected inappropriate shock rate of 0.37 per 100 subject-month, a total of 290 subjects are required to provide approximately 98% power to demonstrate that the inappropriate shock rate is below 2.0% per 100 subject-months. For purposes of sample size calculation, the Type I error rate was set at 0.02 and it was assumed that the subjects had a 2.5-month average prescription wear time.

Sample sizes required to test the primary safety endpoint were lower than those needed for the effectiveness endpoint, so the sample size needed for effectiveness was chosen as the overall sample size.

A site enrollment cap of 20% will be employed in order to ensure no one site dominates enrollment in this trial.

The study is designed to provide data to support the secondary endpoint of demonstration of successful conversion of life-threatening VT or VF episodes. The number of shockable episodes will be monitored over the course of the trial with the goal to observe at least one (1) successful conversion of life-threatening VT or VF with a salvo of up to five (5) shocks.

In order to adjust for a 20% early withdrawal and/or loss to follow-up subjects, a total enrollment of 290/0.80 = 363 subjects may be needed.

9. Poolability Assessment

Site poolability will be assessed using an Rx2 table where each site is a row in the table and the two columns are "number of subjects experiencing an inappropriate shock" and "number of subjects free from inappropriate shocks." Noting that each site had an enrollment cap of approximately 20%, an attempt will be made to test for poolability using a standard Pearson chi-square statistic, however, due to the low probability of receiving an inappropriate shock and the enrollment cap, the table may have many sampling zeros making the Person chi-square statistic invalid. If the standard asymptotic Pearson chi-square test is not valid, exact methods will be used for comparing the sites. A p-value less than 0.15 will indicate that the sites are not poolable and that adjustments for site must be made in the primary endpoint analysis.

10.Sub-group Analyses

The primary effectiveness endpoint of the rate of inappropriate shock will also be analyzed separately for males and females, COVID positive and COVID negative subjects, and for subjects whose BMI is >25 and those with BMI ≤25. Since these sub-groups are not powered, a formal analysis will not be done. Rather the rate of inappropriate shocks will be calculated and 95% two-tailed exact confidence intervals constructed about the rate will be given.

² Olgin JE. et al. Wearable Cardioverter-Defibrillator After Myocardial Infarction. NEJM 2018;379:1205-15

11. Additional Analyses

Jewel System Compliance

All additional analyses will be performed on the primary analysis population.

Subject compliance with using the Jewel will be evaluated using mean weekly wear, wear per device, and time between devices. Mean weekly wear will be measured every 7 days and time between devices will be measured in hours.

The number of hours a subject wears the Jewel during a particular week will be calculated for each subject over the duration of their prescription. The total time between devices will be subtracted from the total wear time, then be averaged for the number of weeks of wear within each subject to provide an average weekly wear time for that subject. The average weekly wear times will then be summarized across subjects using descriptive statistics.

Since each subject will use more than one device over their prescribed time, the time between a subject removing one Jewel and putting on another Jewel will be measured. The device syslog will timestamp transitions between Modes, enabling the calculation of removal time, application time and the time the device transitions the Monitor Mode. Upon availability of the mobile application in the study, the average number of hours for each subject during the transition from one Jewel to another will be calculated. Periods of removal time as attested to by a subject or health care provider and confirmed by electrocardiographic data will be included in the calculation of removal time. These transition times will be summarized across subjects using descriptive statistics.

These measures of compliance will be presented in table format.

Detection of Ventricular Arrhythmias

An analysis of all events that trigger the alarm cycle after three (3) segments of shockable rhythm (~24 seconds) during analyzable wear time will be performed. Each event will be categorized by the type of rhythm or event experienced. These categories of will be summarized in a frequency table showing the number and percentage of times each arrhythmia triggered the alarm cycle.

Quality of Life

A Quality of Life (QOL) measurement tool (EQ-5D-3L) will be used to quantify any impact that the Jewel has on a subjects QOL.

12.Protocol Deviations

Protocol deviations will be summarized in tabular form using the frequency and proportion of each type of deviation observed.

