1. PROTOCOL SUMMARY

1.1 Synopsis			
Title:	The Jewel IDE Study: A Clinical Evaluation of the Jewel P-WCD in Subjects at High Risk for Sudden Cardiac Arrest. ("JEWEL")		
Study Description:	Multi-center, prospective, single arm study of the Jewel Patch-Wearable Cardioverter Defibrillator (P-WCD) System in patients at high risk for Sudden Cardiac Arrest.		
Objective:	To demonstrate the safety and clinical effectiveness of the Jewel P-WCD.		
Endpoints:	Primary Effectiveness Endpoint: To demonstrate an observed inappropriate shock rate of no more than 2.0 inappropriate shocks per 100 patient-months.		
	Primary Safety Endpoint: To demonstrate an observed rate of subjects experiencing a clinically significant cutaneous Adverse Device Effects (ADE) of <15%.		
	Secondary Endpoints:		
	 To observe successful conversion of at least one shockable rhythm with a salvo of up to five (5) shocks. 		
	• To observe a compliance rate of subjects wearing the Jewel of greater than 14.1 average hours per day during a prescription wear period.		
Study Population:	A total of 290 analyzable adult subjects in the United States at risk for sudden cardiac arrest who are not candidates for or who refuse an implanted defibrillator. Specifically, subjects:		
	 a. with a measured left ventricular ejection fraction (LVEF) less than or equal to 40% (as assessed within the last 30 days prior to enrollment) AND identified as presenting with a diagnosis of an acute myocardial infarction (AMI), ischemic cardiomyopathy (includes congestive heart failure NYHA Class I – III), non-ischemic cardiomyopathy, or myocarditis; 		
	OR		
	 who have a temporary or long-term contraindication to receiving an ICD, who have had an ICD removed, or who refuse an ICD. 		
	OR		
	 whose ICD implantation is delayed due to COVID-19 infection or exposure- related risks. 		
Sites, Geographies:	Subjects will be enrolled at up to 60 participating sites in the United States.		
Study Intervention:	Jewel Patch Wearable Cardioverter Defibrillator ("Jewel") System		
	The Jewel is a P-WCD applied directly to a patient's torso in an anterior-apical monitoring vector. The Jewel is worn continuously, 24-hours per day, for up to 8-days per Patch Unit, for the duration of the prescription period.		
Total Study Duration:	18 months		
Subject Participation Duration:	Individual subject participation will be determined by their Investigator but will not exceed 180 days.		

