4. STUDY DESIGN

4.1 Overall Design

This study is a multi-center, prospective, single-arm evaluation of the Jewel P-WCD in adult subjects at risk for sudden cardiac arrest, who are not candidates for or who refuse an implanted cardioverter defibrillator. The study will include up to sixty (60) sites in the United States. This design incorporates one interim analysis at 179 analyzable subjects and one final analysis at 290 analyzable subjects.

There is another analysis point once 100 subjects have completed their prescription wear time, which will be performed to support application for CE mark.

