9.4.7 Study Site Poolability

Site poolability will be assessed using an Rx2 table where each site is a row in the table and the two columns are "number of subjects experiencing an inappropriate shock" and "number of subjects free from inappropriate shocks." Details of the analysis will be outlined in the SAP.

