5.1. Primary Effectiveness Endpoints

All shocks during analyzable wear time will be recorded, centrally evaluated and adjudicated by the Clinical Events Committee (CEC), and reported.

The primary effectiveness endpoint is the rate of inappropriate shock. A one-sided upper 98% confidence limit will be calculated for the inappropriate shock rate per 100 patient-months at the final analysis. Specifically, an intercept-only Poisson regression model will be fit to the data. All wear times through the first inappropriate shock or through death or withdrawal or wear times for subjects without inappropriate shock, death, or withdrawal at the time of analysis will contribute to the Poisson regression model. The one-sided upper 98% confidence limit inappropriate shock rate will be calculated by taking the one-sided upper 98% confidence limit of the intercept parameter in the regression model. The null hypothesis will be rejected if the upper confidence limit on the inappropriate shock rate is less than 2.0.

The formal hypotheses are:

 H_0 : Inappropriate shock rate ≥ 2.0 per 100 patient-months H_a : Inappropriate shock rate < 2.0 per 100 patient-months

The analysis will be re-run on the per protocol analysis population if that population is different from the primary analysis population. Results of this analysis are strictly supportive.

Note that subjects experiencing an inappropriate shock will continue to be followed and accumulate wear time in order to collect data on the other endpoints of this trial.

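### A poolability p-value below 0.15 obliges the primary analysis to adjust for site, but no adjusted model or bounded parameter is named, and with about 2.7 expected events the verdict depends on which one is chosen

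*SAP*

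**What the plan says.** Protocol 9.4.7 sets up the check and leaves the detail to the SAP: "Site poolability will be assessed using an Rx2 table where each site is a row in the table", with subjects split by whether they had an inappropriate shock.

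SAP Section 9 (Poolability Assessment) tries a Pearson chi-square first and foresees that sparse data may invalidate it: "If the standard asymptotic Pearson chi-square test is not valid, exact methods will be used for comparing the sites". The exact method is not named. The consequence is worded as an obligation: a p-value under 0.15 is taken to show that "the sites are not poolable and that adjustments for site must be made in the primary endpoint analysis".

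SAP 5.1 defines the primary test. An intercept-only Poisson model is fitted to time to first inappropriate shock, and the rate limit is obtained by "taking the one-sided upper 98% confidence limit of the intercept parameter in the regression model". Success means a limit below 2.0 per 100 patient-months. SAP 5.5 uses the same analysis with a 97% limit at the interim.

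On the number of sites, Protocol 4.1 states: "The study will include up to sixty (60) sites in the United States". SAP Section 8 adds a 20% enrollment cap per site. Nothing else is said about site sizes.

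**The concern.** Section 9 changes the confirmatory model on the strength of a preliminary test, but does not say to what. In an intercept-only model the intercept is the log of the trial's overall rate. Once site terms are added it may be one reference site's log rate, a conditional mean across sites, or still the overall rate with a different standard error, depending on the method. The SAP names neither the method nor the parameter whose limit is to be compared with 2.0. It anticipates sampling zeros for the poolability test, but not for the adjusted model that must follow.

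The preliminary test will sometimes fire with no site heterogeneity at all. In those trials a valid pooled result is set aside, and the analyst of an open-label single-arm study must pick a model with the events already known. Success rests on a single confidence limit, so that choice can decide the trial.

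**Working it through.** **Inputs.** From SAP Section 8: 290 subjects, wear time normal with mean 2.5 and SD 0.5 months, shock rate 0.37 per 100 subject-months, one-sided alpha 0.02, and zero events replaced by 0.5 in the simulations. From SAP 5.1: performance goal 2.0. From SAP Section 9: threshold 0.15. From the protocol: up to 60 sites. Assumed: how subjects are spread over sites.

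**1. Reproduce the plan's power.** Expected events are about 290 × 2.5 × 0.0037 = 2.68, or 2.67 after stopping exposure at the first shock. With d events in T = 290 × 2.5 = 725 months, the Poisson (Wald, log-scale) limit per 100 months is 100 × (d/T) × exp(2.054/√d).

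| d | limit | result |
|---|---|---|
| 3 | 1.35 | pass |
| 6 | 1.91 | pass |
| 7 | 2.10 | fail |

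Zero events, counted as 0.5, gives 1.26 and passes. Success therefore needs at most 6 events. Simulated power is 98.1%, which agrees with the stated figure of about 98%. Interim power at 179 subjects is 83.5%, which agrees with the protocol's figure of more than 83%. Neither calculation includes the poolability step.

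**2. How often the rule fires when sites are homogeneous.** About 6.8% of trials have no event and cannot trigger. A valid exact test at 0.15 therefore fires in at most about 0.15 × 93% = 14% of trials. Simulation with exact tests at 290 subjects gave:

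- equal or near-equal site sizes, 10–60 sites: about 4–9%;
- uneven sizes (linear, 1/rank or geometric, capped at 20%), 10–60 sites: about 12–14%;
- at the interim (179 subjects, 1.65 events expected): 2.4–12%.

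The asymptotic chi-square would give about 6–30%, but the SAP drops it when it is invalid.

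**3. One triggered trial by hand.** Take 29 sites of 10 subjects, three events, two of them at one site. The exact p-value is the chance that three events do not all fall at different sites: 1 − (280/289) × (270/288) = 0.092. The rule fires. Using 25 months of exposure per site:

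- *Pooled model:* rate 3/725 = 0.414 per 100 months, limit 1.35. Pass.
- *Fixed site terms, zero-event reference site:* intercept about −26, standard error about 59,000. No usable limit.
- *Cluster-robust variance:* each site expects 3/29 = 0.103 events. Squared residuals sum to 4.69. The standard error is (√4.69/3) × √(29/28) = 0.735 and the limit is 0.414 × exp(2.054 × 0.735) = 1.87. Pass.
- *Gamma random site effect, fitted numerically:* standard error of the log rate 0.811, limit 0.414 × exp(2.054 × 0.811) = 2.19. Fail.

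The same data give a pass, a fail or no answer, and the SAP does not say which applies.

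**4. Across triggered trials.** In simulations with 30 and 60 sites, triggered trials averaged about 3 events; with 60 sites about 57 had none. Shares with a limit below 2.0 were:

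| analysis | pass |
|---|---|
| pooled, unadjusted | 96–98% |
| cluster-robust | 78–95% |
| gamma site effect | 7–56% |

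A fixed-site Poisson fit to 60 sites with three events gave an intercept standard error of about 139,000 and no usable limit.

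**5. Effect on power.** If every triggered trial failed at the final look, with uneven sites and a 13% trigger rate, power there would be about 98.1% × (1 − 0.13) = 85%. Counting both looks, and still failing every triggered look, effectiveness success is about 91–92% with uneven sites and 95–96% with equal sites, against about 98.5% without the rule. The interim safety condition is not modelled.

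**The case against.** The strongest reply is that Section 9 does not prescribe fixed site indicators. The infinite limit comes from one parameterisation; a cluster-robust or random-site analysis can be fitted to the same data and returns a finite limit. This stands. A reader might infer that the primary test cannot be computed once the rule fires, and the documents do not support that. They support only that it is undefined until someone chooses a method.

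A reader might also infer a fixed trigger rate of about 13%, or a fall in power to 85%. Neither follows from the documents. The first needs uneven sites. The second also needs every triggered trial to fail, and it ignores the interim look.

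Nor does the rule always fire on small coincidences. With 10 equal sites of 29, two of three events at one site gives p = 1 − (261/289) × (232/288) = 0.27. With 20 or 40 near-equal sites a single event cannot trigger it.

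Finally, the SAP expects sparse tables and switches to exact methods. That repairs the validity of the poolability test. It does nothing for the adjusted analysis that the test then requires. The wide spread of pass rates among estimable adjustments is what keeps the concern alive.

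**Conclusion.** The concern holds as a gap in pre-specification with material consequences. The SAP makes site adjustment mandatory on a p-value that falls below 0.15 in roughly 4–9% of homogeneous trials with equal sites and 12–14% with uneven ones. It then names no model and no parameter to bound. With about 2.7 expected events and at most 6 compatible with success, the reasonable candidates can disagree on the verdict, so that verdict would rest on a post-hoc choice.

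The stated 98% power is correct for the pooled test, but not for the procedure as written. The size of the loss depends on the adjustment chosen, and about 85% is only the worst case at the final look.

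These figures assume the SAP's own rate and wear-time model, an exact poolability test, and site sizes that the documents do not give.

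**What to change.** Keep the pooled intercept-only rate as the primary test whatever the poolability p-value. Replace the mandatory adjustment in SAP Section 9 with pre-specified sensitivity analyses:

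- the rate and its limit with each site left out in turn;
- a Poisson model with a random site effect that reports the marginal rate, with small sites combined by a rule fixed in advance.

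Name the exact poolability test and say what is done when there are no events.

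If the sponsor prefers to keep an adjustment in the primary analysis, the SAP should name in advance one that can be estimated with this few events, and state that the limit compared with 2.0 is that of the marginal rate. It should also say whether the rule applies at the interim, and the power simulation should be rerun with the step included.

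The preferred option costs one paragraph of SAP text and two small analyses, with no change to conduct or sample size. Its downside is that site heterogeneity is described and no longer acted on automatically. With so few events, little more can be supported.
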